2.8 STUDY ENDPOINTS

Principle Outcomes: The principle objectives for the pilot trial are to evaluate 1.) safety and efficacy and 2.) feasibility for a prehospital through in-hospital LTLR-WB resuscitation protocol that will lead to a large, multicenter clinical trial that can be performed under the requirements of *exception from informed consent for emergency research* with regulatory oversight by the Food and Drug Administration (FDA) and Title 21, Code of Federal Regulations, Section 50.24 (21 CFR 50.24).

Primary Outcome For Assessing Safety and Efficacy: The primary safety and efficacy outcome for the pilot trial will be all cause 28-day mortality. We will utilize data derived from our recently completed PAMPer trial, which utilized identical inclusion and exclusion criteria, for inhospital mortality estimates.

Primary Outcome For Assessing Feasibility and Trial Performance: The primary feasibility outcome for the pilot trial will be enrollment and accrual rate. Secondary performance and feasibility outcomes will include a) Eligibility rates; b) Adherence rates for the protocol; c) Injury and patient characteristics enrolled in the trial; d) Frequencies of proposed clinical outcomes; e) Air medical base population differences.

Secondary Clinical Outcomes Estimating Treatment Effectiveness and Safety: Over 28 days or up to discharge following randomization, we will compare: 1) Multiple Organ Failure (MOF): Organ dysfunction will be evaluated via the Denver Post-Injury Multiple Organ Failure Score and characterized as both a rate (%) and as MOF free days.^{84,85} 2) Mean Denver Post-injury MOF Score: This continuous variable will be a much more sensitive measure of organ dysfunction for the pilot trial. 3) Arrival Shock Severity: We will compare presenting base deficit,

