Multiple Organ Failure (MOF): Organ dysfunction will be evaluated via the Denver Post-injury Multiple Organ Failure Score, a well-validated scoring system in injured patients and characterized as an incidence rate (%) and as MOF free days.^{84,87} Patients who are never admitted to the ICU or those with a length of ICU stay of less than 48 hrs will be considered to have a Denver score of 0. A summary of the Denver score may be calculated by summing the worst scores of each of the individual systems over the course of the ICU stay. A summary Denver score > 3 will be classified as MOF. Scores will be determined daily up until ICU discharge.⁸⁷ Mean Denver Post-injury MOF Score: As the primary endpoint for the pilot trial, the 3 highest (worst) daily Denver scores will be averaged and compared across the treatment arms. Patient not in the ICU will be given a score of 0. Acute Respiratory Distress Syndrome (ARDS): The Berlin definition for mild ARDS (PaO_2/FIO_2 , ≤ 300 mm Hg + timing, imaging and origin criteria) will be utilized as a threshold value to determine the incidence of ARDS and will be further stratified into Moderate (PaO_2/FIO_2 , ≤ 200) and Severe (PaO_2/FIO_2 , \leq 100).⁸⁶(Nosocomial Infection (NI): The CDC criteria for the diagnosis of hospital acquired pneumonia and blood stream infection will be utilized (www.cdc.gov/nhsn) Mortality: We will derive the time to a mortality event from the time of admission for 6 hour and 24 hour mortality rates over the initial 24 hours. All cause in-hospital and 28-day mortality will be similarly determined from the date of admission. 7) Blood component transfusion and resuscitation requirements at 24 hours: Blood component transfusion needs per unit (PRBC, FFP, PLT) will be recorded over the first 24 hours of admission with 6-hour incremental totals. For every unit of LTLR-WB that is transfused each will be designated as 1 unit of PRBC, 1u of FFP and a single pack of platelets. Similar recording of crystalloid volume and colloid volume of the initial 24 hours following admission will be undertaken. 8) Acute Hemolytic Transfusion Reactions: We will compare the incidence AHTRs (CDC NHSN Hemovigilance Surveillance definition) and will measure arrival serum haptoglobin levels. 9) Length of hospital and intensive care unit (ICU) stay: Length of stay will be determined from the date of admission for all enrolled patients.

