2.9 STATISTICAL ANALYSIS

The overarching goals for the pilot trial are to evaluate safety, efficacy and feasibility of a LTLR-WB prehospital through in-hospital protocol to plan for the successful execution of a large, multicenter clinical trial. All analyses will be performed based on the intent-to-treat principle for the prehospital randomization and analyses will include all enrolled patients grouped by randomization assignment. This pilot study will guide the calculation needed for the large, multicenter clinical trial and will provide estimation for intra-cluster correlation coefficient and sample size variation across clusters. We will report 95% confidence intervals for all measurements

Safety and Efficacy Analysis: 28-day mortality is the primary safety and efficacy outcome and will be compared across randomized groups. Utilizing intention to treat principles we will compare the LTLR-WB and Standard of Care arms using a pooled Z test for comparing two independent proportions. We will additionally perform survival analysis for all mortality outcomes including 3hr, 6hr, 24hr, and 28day time points across the two arms of the study testing the differences using log rank test.

Eligibility, Enrollment, and Subject Accrual Anlaysis: The feasibility of enrollment will be evaluated by determining 1) the number of patients that meet the eligibility criteria for the trial; 2) the proportion of eligible patients that can be randomized and 3) the proportion of eligible patients who are enrolled in the trial. These proportions will be estimated directly as the observed ratio of numbers of patients, and 95% confidence intervals will be calculated to understand the likely range of values for a larger study with a comparable research protocol. The reasons why patients are not enrolled including frequencies of individual exclusions and the proportion of patients declining participation or not able to be randomized will be described. Rate of subjects' accrual per month with 95% C.I. will be calculated.

Adherence and Minimization of Bias: Adherence rates for each treatment arm of the protocol will be ascertained as the proportion of enrolled patients who adhere to the intervention (LTLR-WB vs. standard care) as assigned. Estimated proportions and 95% confidence intervals will be created. The trial has been designed to negate intervention arm crossover and maximize follow-up completion.

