Estimates for Trial Secondary Clinical Outcomes: We will estimate the mean differences in the average Denver post-injury MOF score derived from the 3 highest daily scores between two treatment groups as the main clinical outcome for the pilot trial. We will also record and compare the overall proportion of patients who developed MOF based on Denver score > 3 and compare MOF free days. Similarly, the incidence of ARDS, NI, mortality (6hr, 24hr and 28 day) and hemolytic transfusion reactions will be recorded. We will perform survival analysis for all mortality outcomes. Blood component and resuscitation volumes over the initial 24 hours, length of ICU stay, days on a ventilator, and total hospital stay will be also be determined. Estimated proportions and means and 95% confidence intervals will be created for each outcome using the data from the entire pilot trial (i.e. combining the data from the two assigned treatment arms). Absolute and relative differences for continuous levels and event rates by assigned treatment will be estimated and 95% confidence intervals will be calculated to identify potential treatment differences for safety and for study planning purposes. Subgroup analyses will be exploratory and be based on baseline factors specified prior to the initiation of the trial.

The Following Outcomes Will Be Recorded:

- 1. The average Denver post-injury MOF score derived from the 3 highest daily scores. Differences between these averages will be estimated across the study two arms.
- Proportion of patients who developed MOF based on Denver score > 3 and compare MOF free days across the study two arms.
- 3. The incidence of ARDS, NI, mortality (6hr, 24hr and 28 day) and hemolytic transfusion reactions will be recorded and compared across the study two arms
- 4. Survival analysis in relation to all causes of death.
- 5. Blood component and resuscitation volumes over the initial 24 hours,
- 6. Length of ICU stay, days on a ventilator, and total hospital stay will be also be determined.

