If the PI and study team plan to modify the study, they will submit the amendment to the University of Pittsburgh HRPO along with all study documents to be changed (i.e. protocol, consent form, etc.) Once IRB approval is obtained, the study team will submit the changes to the NIH at the next reporting cycle unless earlier notification is warranted. If it is a significant change, the PI will request approval by the NIH Program Officer and DSMB prior to modification. Any changes will also be reviewed by the Office for Investigator-Sponsored IND and IDE Support (O3IS) for determination if the change requires prospective FDA review or if it can be submitted at annual report.

Data Analysis Plan Overall guideline:

- 1. Nature of this study: Pilot study
- 2. Overall objectives: Evaluate safety, efficacy, and feasibility of a LTLR-WB prehospital thru in-hospital protocol. The study will provide estimation for intra-cluster correlation coefficient and sample size variation across clusters for the design for a future full scope large clinical trail
- 3. Analysis Principle: Intent-to-treat for the prehospital randomization assignment. 95% confidence intervals for all measurements

Safety and Efficacy Analysis:

- 1. In-hospital mortality is the primary safety and efficacy outcome and will be compared across randomized groups.
- 2. LTLR-WB and Standard of Care arms will be compared using a pooled Z test of two independent proportions.
- 3. Survival analysis will be conducting looking at median survival at 3hr, 6hr, 24hr, and 28day time points across the two arms of the study testing the differences using log rank test.

Eligibility, Enrollment, and Subject Accrual:

The feasibility of enrollment will be evaluated by determining, ratio of the following parameters will be calculated along with 95% confidence intervals:

- 1) the number of patients that meet the eligibility criteria for the trial;
- 2) the proportion of eligible patients that can be randomized and

3) the proportion of eligible patients who are enrolled in the trial.

Additionally:

1. The reasons of not enrollment will be recorded with related frequency and percentages.

- 2. Frequency of patients eligible but not enrolled will be recorded
- 3. Frequency of patients randomized but not included in the study will be recorded
- 4. Rate of subjects' accrual per month with 95% C.I. will be calculated.

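### Section 2.8 labels the mean Denver organ-failure score the pilot's primary endpoint, contradicting a plan that otherwise makes mortality primary and the Denver score secondary

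*Combined protocol and SAP*

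**What the plan says.** **Text that raises the Denver score.** The Clinical Outcome Definitions in section 2.8 state: "As the primary endpoint for the pilot trial, the 3 highest (worst) daily Denver scores will be averaged and compared across the treatment arms". Section 2.9 estimates the mean difference in the same score "between two treatment groups as the main clinical outcome for the pilot trial". That sentence stands under the heading "Estimates for Trial Secondary Clinical Outcomes".

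**Text that makes mortality primary.** Section 2.8 says: "The primary safety and efficacy outcome for the pilot trial will be all cause 28-day mortality". Section 2.9 says: "28-day mortality is the primary safety and efficacy outcome and will be compared across randomized groups", and names a pooled Z test. The data analysis plan in section 6.4.2 also makes mortality primary, but a different mortality endpoint: "In-hospital mortality is the primary safety and efficacy outcome and will be compared across randomized groups".

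**Text that makes the Denver score secondary.** In section 2.8 the mean Denver score is item 2 of the secondary clinical outcomes, with the comment "This continuous variable will be a much more sensitive measure of organ dysfunction for the pilot trial".

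**Design elements.** The sample size in section 2.9, repeated in section 6.4.7, uses in-hospital mortality: 33% versus 11%, 56 patients per arm, two-sided alpha 0.05, 80% power, two O'Brien-Fleming looks. The stopping rules in section 6.4.2 apply to in-hospital mortality. Appendix 8 puts in-hospital mortality in Table 2 with a Z test. It puts the Denver score in Table 4, the secondary-outcome table, with a confidence interval column and no test.

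No section gives a hierarchy, an alpha split or a co-primary rule linking the two endpoints.

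**The concern.** The phrase in section 2.8 is part of the definition from which the Denver endpoint will be computed, so it is not a passing remark. Taken at its word, the pilot has a primary clinical endpoint with no assumed difference, no standard deviation, no power calculation and no share of alpha, alongside a mortality endpoint that already spends the full 5%. If mortality were not significant and the Denver difference looked favourable, an author could cite section 2.8 to present the Denver result as the trial's primary finding. The same holds with the roles exchanged.

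The choice could matter for direction as well as significance. Under the organ-failure definition in section 2.8, a patient never admitted to the ICU, or with an ICU stay under 48 hours, scores 0. The mean-score definition repeats the zero for patients not in the ICU. Early deaths can therefore receive the best possible Denver score, and a treatment that averts early deaths could lower mortality while raising the mean Denver score.

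**Working it through.** **1. Which endpoint the design was sized on.** Inputs from sections 2.9 and 6.4.7: control risk 0.33, treated risk 0.11, 56 per arm, boundaries 2.96259 and 1.96857 at information 0.50 and 1.00.

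- Pooled risk = (0.33 + 0.11)/2 = 0.22.
- Drift = 0.22 / √(2 × 0.22 × 0.78 / 56) = 2.8102. The plan states 2.81024.
- Power at look 1 = 0.1647 and total power = 0.8010. The plan states 0.164669 and 0.800921.
- Nominal alphas = 0.003051 and 0.049002; total alpha = 0.0500. These match the plan.

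The plan's figures reproduce from mortality alone. The mortality comparison uses the full two-sided 5%, and that error rate is correct as stated.

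**2. What would follow if either endpoint could carry the claim.** This is hypothetical: the plan states no such rule and no Denver test. Assume the Denver difference is judged at two-sided 5%, in line with the 95% intervals that section 2.9 applies to all measurements. Let ρ be the correlation of the two test statistics. The documents give no value, so a range is shown.

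P(at least one false positive) = 1 − P(|Z_mortality| ≤ c and |Z_Denver| ≤ 1.96). With a single look and ρ = 0 this is 1 − 0.95 × 0.95 = 0.0975. The upper bound is 0.05 + 0.05 = 0.10. The two-look column uses the plan's mortality boundaries and a final Denver test at 1.96 (4,000,000 simulated null trials per row).

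| ρ (assumed) | Single look | Two-look mortality |
|---|---|---|
| 0 | 9.75% | 9.74% |
| 0.3 | 9.51% | 9.51% |
| 0.5 | 9.07% | 9.08% |
| 0.7 | 8.35% | 8.37% |
| 0.9 | 7.04% | 7.06% |

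At ρ = 0.5, under the null, the two endpoints would give different verdicts in 2 × 9.1% − 10% = 8.2% of trials. Section 6.4.2 also has secondary outcomes checked at the interim with 95% intervals. If the Denver score were judged at 1.96 there too, a further assumption, the error would be about 12.9% at ρ = 0 and 12.1% at ρ = 0.5. None of these figures allows for randomisation by helicopter base.

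**3. Keeping both as primary.** With a Bonferroni split at 0.025 each, two-look power for mortality at 56 per arm falls from 80% to 71.4%. About 68 per arm would be needed to restore 80%.

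**4. Can the directions differ?** An illustration with assumed values: control mortality 33%, half of the deaths early and scored 0, the other deaths scoring 2.5, survivors averaging 1.0.

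- Control mean = 0.165 × 0 + 0.165 × 2.5 + 0.67 × 1.0 = 1.08.
- Avert 10 percentage points of early deaths, with those patients then scoring 2.0: add 0.10 × 2.0 = 0.20, giving 1.28.

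Mortality improves while the Denver mean worsens. The reversal cancels if the 67% who survive in any case improve by 0.20/0.67 ≈ 0.30 points.

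**The case against.** The strongest reply is that the plan as a whole already ranks the endpoints. Only mortality has a named test, an alpha, a power calculation and stopping boundaries. The Denver score is estimated with an interval, and section 2.9 gives the purpose of such intervals as spotting possible safety differences and planning a later trial. Its description as the main clinical outcome sits under a secondary-outcomes heading and can be read as the main one among the secondaries. Appendix 8 follows the same ranking. Section 2.9 also mentions originally planned feasibility outcomes and an enlarged sample, which is compatible with the Denver label being left over from a previous design, though that is inference.

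Most of this stands. A reader might infer that the plan lets two endpoints each decide the trial at full 5% alpha, or that its 5% error rate fails. The documents do not support either reading: they give no Denver test, threshold or success rule, and the stated 5% belongs to mortality, where it reproduces. The general 95% intervals cover every measurement and do not mark the Denver score as confirmatory.

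The example of opposite directions rests on chosen inputs. It also assumes no Denver benefit in other patients, although Specific Aim II hypothesises less organ dysfunction.

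The reply does not remove the clause in section 2.8. It is unambiguous, nothing retracts it, and it contradicts the list of secondary outcomes in the same section.

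**Conclusion.** The contradiction is real but narrower than a loss of error control. Section 2.8 attaches a primary label to the mean Denver score, and section 2.9 gives weaker support. Both conflict with the stated primary mortality outcome, the mortality-only sizing and boundaries, and the Appendix 8 tables. Because the label is in an operative endpoint definition and permits selective emphasis after the results are known, it is more than a clerical slip.

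The inflation to between about 7% and 9.8% depends on an either-endpoint rule, a Denver test at two-sided 5% and an assumed correlation, with clustering ignored. It measures what the ambiguity could cost if used that way and is not a property of the plan as written. Disagreement in direction is a possibility, not a likely result.

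**What to change.** 1. In the Clinical Outcome Definitions of section 2.8, delete the opening clause of the mean Denver definition, the one that calls it primary.
2. In section 2.9, replace "as the main clinical outcome for the pilot trial" with wording that makes it a secondary clinical outcome, reported as an estimate with a 95% CI.
3. State once that a single named mortality endpoint, compared by the pooled Z test at the O'Brien-Fleming boundaries, is the only confirmatory clinical comparison, and that a Denver result cannot be reported as the primary finding.
4. Name that mortality endpoint and use it throughout. Sections 2.8 and 2.9 (Safety and Efficacy Analysis) name 28-day mortality. The sample size text in section 2.9, the analysis plan and interim rules in section 6.4.2, section 6.4.7 and Appendix 8 Table 2 use in-hospital mortality. Without this step the statement in item 3 has no defined object.

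Items 1 to 3 are wording changes that need no patients or data and leave the stated 80% power as it is. Item 4 also needs a decision, and the sample size text must then refer to the endpoint chosen. The cost is that a favourable Denver result can be claimed only as secondary. The scoring of early deaths as 0 is a separate matter that these edits leave in place.

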1.2 SPECIFIC AIMS

Hypothesis: The initiation of LTLR-WB resuscitation in the prehospital setting with continuation through the in-hospital acute resuscitation phase of care will significantly reduce the morbidity and mortality attributable to hemorrhagic shock post-injury as compared to standard prehospital and in-hospital resuscitation practice.

Specific Aims:

Specific Aim I: Determine the feasibility and most appropriate study population that will lead to a large multicenter clinical trial designed to evaluate the effectiveness of prehospital through inhospital LTLR-WB as compared to standard care practice in patients at risk of hemorrhagic shock.

Specific Aim II: Determine if prehospital through in-hospital LTLR-WB reduces 28-day mortality, in-hospital mortality, multiple organ dysfunction, presenting coagulopathy, 24-hour resuscitation requirements and early mortality as compared to standard of care prehospital and in-hospital resuscitation in patients at risk of hemorrhagic shock.

Specific Aim III: Determine the primary drivers by which prehospital through in-hospital LTLR-WB improves clinical, resuscitative and hemostatic outcomes as compared to standard of care prehospital and in-hospital resuscitation in patients at risk of hemorrhagic shock.

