2.4 INTERVENTIONAL ARM

Prehospital Phase Interventional Arm: Two units of LTLR-WB (O+) will be stored at each helicopter base in temperature regulated blood bank approved refrigerators for up to 14 days, which is the period within which cold stored platelets are thought to retain maximal function. Two units of LTLR-WB will be transported on all air medical flights with prehospital staff in blood banking approved and verified coolers. The temperature of the blood will be monitored throughout transit and storage in accordance with standard blood banking and Stat MedEvac procedures. Following 14 days without use, LTLR-WB will be replaced with new LTLR-WB units and the old products will be returned to the blood bank for recycling into PRBCs.. During transport, storage and during all flights standard STAT MEDEVAC protocols for storing and carrying blood products at the base and on the helicopters will be followed. While at the bases the blood units are stored in a dedicated blood refrigerator and moved to cooler for transport only when the aircraft is launched. The blood is packaged in the coolers with a thermometer for temperature maintenance to assure that they are maintained at 2-5 degrees Celsius at all times. The Clinical Protocol that is currently followed and will be followed for all blood products in the study can be found in Appendix 1. Our FDA approved blood bank will follow all regulations required by the FDA for safe blood and blood component transfusion. On day 15, after ensuring the WB unit had remained in temperature compliance and is otherwise eligible for recycling according to 21 CFR 640.2(c), the WB unit will be recycled into a PRBC unit following the standard operating procedures at the Centralized Transfusion Service in Pittsburgh.

Patients who meet all inclusion and no exclusion criteria at the scene, at a referral hospital or during transport and are randomized to the interventional arm will receive up to 2 units of LTLR-WB (O+) en-route to a PPOWER participating trauma center based upon hemodynamic status using identical criteria as the Prehospital Standard of Care arm. If the intervention is completed during transport, standard operating procedures for the prehospital setting will be employed by the prehospital providers during the remaining flight. (Appendix 7)

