lactate and shock index (SI, heart rate/systolic blood pressure-bpm/mmHg) 4) Acute Respiratory Distress Syndrome (ARDS): We will compare pulmonary dysfunction using the Berlin definition for ARDS.⁸⁶ 5) Nosocomial Infection (NI): We will compare the incidence of pneumonia and blood stream infections. 6) Mortality: We will compare mortality rates at 3, 6 and 24 hours following arrival, all cause in-hospital and 28-day mortality. 7) Blood component transfusion and resuscitation requirements at 24 hours: We will compare overall blood component transfusion requirements and crystalloid/colloid resuscitation requirements across the two arms. 8) Acute Hemolytic Transfusion Reaction (AHTR): We will compare the incidence of AHTRs across study arms as defined by the CDC/National Healthcare Safety Network (NHSN) Hemovigilance Surveillance definition. (www.cdc.gov/nhsn) Length of hospital stay and intensive care unit stay. Length of stay and ICU resources will be descriptively compared. Patients will be followed for 28 days from admission for the 28-day mortality outcome utilizing chart review, patient contact or utilization of the social security death index for those who cannot be contacted.

Predefined Subgroup Analyses: Predefined subset analyses for the pilot trial will be performed looking at our primary outcomes (safety/efficacy and feasibility) in 1) Females > 50 years of age versus study cohort with females < 50 years excluded ; 2) Patients who ultimately did or did not require in-hospital blood transfusion; 3) Patients with and without significant traumatic brain injury (Head abbreviated injury score- AIS >2); 4) Patients enrolled from the scene of injury versus those enrolled from a referral hospital; 5) Patients that require operative intervention in the first 24 hours; 6) Those patients with a preinjury history of anticoagulation / antiplatelet therapy; 7) Patients who ultimately did or did not require massive transfusion (≥ 10 units blood in first 24 hrs) 8)Patients who did or did not receive prehospital PRBCs.

Clinical Outcome Definitions:

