6.3 POTENTIAL BENEFITS

We anticipate that the benefits of getting whole blood may reduce bleeding in some patients, and possibly reduce overall blood transfusion requirements during the first day after injury. Prior studies have suggested that early whole blood transfusion may improve outcomes in patients with a lot of blood loss. Whether the subject receives the early whole blood transfusion, s/he may also benefit from increased observation at the time points involved in the study. Ultimately subject participation may help us to improve prehospital treatment of trauma injuries.

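### The 24-hour blood and fluid totals for Specific Aim II start at admission and so omit prehospital treatment, which for blood products differs between the arms

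*Combined protocol and SAP*

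**What the plan says.** Section 1.2 (Specific Aim II) compares the two strategies, each running from the prehospital phase into the hospital, on "24-hour resuscitation requirements and early mortality as compared to standard of care prehospital and in-hospital resuscitation". Section 6.3 puts the hoped-for benefit in similar terms: whole blood may "possibly reduce overall blood transfusion requirements during the first day after injury".

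Section 2.8 handles the outcome twice. The list of secondary clinical outcomes opens with a period counted from randomization, and its seventh item compares "overall blood component transfusion requirements and crystalloid/colloid resuscitation requirements across the two arms". The Clinical Outcome Definitions then give the only operational rule. Blood components "will be recorded over the first 24 hours of admission with 6-hour incremental totals". For whole blood, "each will be designated as 1 unit of PRBC, 1u of FFP and a single pack of platelets". Recording of "crystalloid volume and colloid volume of the initial 24 hours following admission will be undertaken". Section 2.9 lists "Blood component and resuscitation volumes over the initial 24 hours" without saying when the 24 hours begin, and Appendix 8, Table 4 likewise gives no start.

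Treatment under the assignment starts earlier. Section 2.4 says that intervention patients "will receive up to 2 units of LTLR-WB (O+) en-route to a PPOWER participating trauma center", out of a maximum of 8 units. Section 2.5 gives controls prehospital crystalloid and PRBC, with no number of units. Appendix 4 also describes en-route standard care as crystalloid and red cells, with component resuscitation after arrival.

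**The concern.** The aim concerns the whole strategy, but the definition counts only what is given after the door of the trauma center. For blood products, the uncounted part is where the arms first diverge: whole blood on one side, crystalloid and red cells on the other. Blood given in flight leaves the total, so a patient whose need has only been met earlier can look like a patient who needed less. An Aim II result could then be read as a saving when part of it is a shift in timing. Because this pilot is meant to inform a large multicenter trial, the definition would also carry into the planning estimates.

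**Working it through.** The plan states no effect size, precision or power for this outcome, so there is no figure to reproduce. The check is unit arithmetic with the plan's own conversion.

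**Inputs**
- Prehospital LTLR-WB: 0 to 2 units; study maximum 2 + 6 = 8 (section 2.4).
- Conversion: 1 LTLR-WB = 1 PRBC + 1 FFP + 1 platelet pack (section 2.8).
- Control prehospital blood: PRBC, number not given (section 2.5).
- 56 patients per arm (section 2.9).

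**1. What the window omits.** At 2 in-flight units, 2 PRBC, 2 FFP and 2 platelet packs go uncounted. That is 2/8 = 25% of the whole-blood maximum. It is not 25% of the 24-hour requirement, which also includes components given beyond 8 units.

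**2. Omitted difference between arms.** Let u be mean prehospital LTLR-WB units (0 to 2), and let m and c be mean prehospital PRBC in the LTLR-WB and control arms.
- PRBC: u + m - c. Only the range of u is known. The term m may exceed zero, because section 2.4 returns to standard prehospital procedures once the study units are finished.
- FFP and platelets: u each, on the assumption that controls receive none before arrival. Sections 2.5 and Appendix 4 name none, but section 2.5 does not present its list as complete.
- Crystalloid: not computable.

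**3. Equal-need illustration.** Suppose both arms need the same T red-cell units from enrollment, with a units of LTLR-WB given in flight and b units of PRBC given to controls in flight. The counted difference (whole blood minus control) is (T - a) - (T - b) = b - a. With a = 2:

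| Control prehospital PRBC (b) | Counted difference | Example, T = 8 |
|---|---|---|
| 0 | -2 | 6 vs 8 |
| 1 | -1 | 6 vs 7 |
| 2 | 0 | 6 vs 6 |

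The result does not depend on T.

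**4. Scale against the trial's precision.** The 95% confidence interval half-width for a difference in means is t(0.975, 110) × sqrt(2/56) × SD = 1.982 × 0.189 × SD, or 0.3745 × SD, ignoring clustering. The documents give no SD, so the values below are assumptions.

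| Assumed SD (units) | Half-width | 1 omitted unit as share of half-width |
|---|---|---|
| 3 | 1.12 | 89% |
| 5 | 1.87 | 53% |
| 8 | 3.00 | 33% |

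**5. What a wider window does to the converted totals.** Take two patients who each receive 2 red-cell-containing units in flight and nothing later. Counted from air medical care, the whole-blood patient scores 2 PRBC, 2 FFP and 2 platelet packs; the control scores 2 PRBC, 0 and 0. Widening the window removes the omission, but it makes converted FFP and platelets higher in the whole-blood arm by construction.

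**6. A minor, separate point.** Section 6.4.2 and Appendix 8, Tables 2 and 4, summarize survival by a median. Reaching it needs at least 28 deaths among 56. The binomial probability is 0.0062 at 33% mortality and about 5 × 10⁻¹³ at 11%, the two planning rates.

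**The case against.** The strongest reply is that section 2.8 does supply an earlier origin, because its list of secondary outcomes runs from randomization and speaks of overall requirements. That stands in part. It shows two passages that disagree, and it counts against any suggestion that prehospital product was left out deliberately. It does not settle the matter, since the detailed definition is what an analyst would program.

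An admission-based total is also a legitimate outcome: need after arrival may be a consequence of prehospital treatment. That stands, and the total should be kept, but alone it does not answer Aim II. Nor is a wider window neutral, as step 5 shows. That also stands and shapes the fix.

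The mechanistic outcomes in section 2.8 do compare transfusion volume over the prehospital and acute in-hospital phases. This covers part of the gap. It is not a 24-hour total, it does not include crystalloid, and it is not the Aim II outcome.

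One could prefer enrollment as the origin, since a patient may qualify only during transport. But section 2.6 fixes each base's arm in advance, and section 5.1 allows enrollment after arrival in the emergency department. An enrollment origin would drop all in-flight product for those patients.

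Four stronger readings are tempting but unsupported:
- **That the window favors whole blood by a known amount.** The control PRBC figure is missing, and the conversion credits FFP and platelets to every in-hospital LTLR-WB unit as well, so the net direction is open.
- **That crystalloid differs by design.** Section 2.7 sets a goal-directed procedure after randomization without distinguishing the arms.
- **That the base stock log in Appendix 1 proves controls get no plasma or platelets in flight.** The log is written for PRBC and does not mention whole blood either.
- **That the massive-transfusion subgroup is misclassified differently by arm.** If the admission window were used there, 2 prehospital plus 8 in-hospital units would count as 8, below the threshold of 10. The same holds for a control given 2 prehospital PRBC.

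**Conclusion.** The concern holds as a mismatch between Aim II and its only operational definition. Both totals start at admission, no section adds prehospital amounts to them, and section 2.8 is not consistent with itself on the origin. Up to 2 PRBC, 2 FFP and 2 platelet equivalents per LTLR-WB patient are uncounted, against an unstated amount of control PRBC. For equal total need, this can look like a lower requirement with whole blood. The red-cell range of -2 to 0 assumes 2 in-flight LTLR-WB units and 0 to 2 control PRBC; the comparison with the confidence interval rests on assumed SDs. The net PRBC and crystalloid differences remain unknown, and a difference by design is shown for blood products only. The outcome is secondary and estimated for planning, so the primary test, power and sample size do not change.

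**What to change.** - In the Clinical Outcome Definitions of section 2.8, define the Aim II requirement as all blood products and fluids from the start of air medical care through 24 hours after admission, identically in both arms, and reconcile this with the secondary-outcome list.
- Show admission-to-24-hour totals alongside. Report products given at a referring hospital before air medical care separately.
- Report LTLR-WB units and actual components separately as well as converted, so that FFP and platelets credited by the conversion can be told from those given as components.
- State the same window in section 2.9, in Appendix 8, Table 4, and for the exploratory massive-transfusion subgroup.
- Separately, in section 6.4.2 and Appendix 8, Tables 2 and 4, replace median survival with Kaplan-Meier survival percentages and 95% confidence intervals at the stated times, keeping the log-rank test.

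The cost is wording and table shells. Section 6.5.1 already collects prehospital resuscitation volumes, and the prehospital transfusion record in section 6.4.6 already lists components and units. There are two downsides: the window gains a transport time that varies between patients, and converted FFP and platelet totals rise in the LTLR-WB arm by construction, which the separate reporting makes visible.
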